1. PURPOSE

To determine the feasibility of establishing patient-derived organoids from pre-treatment rectal adenocarcinoma biopsies.

Primary Objective(s):

1. To determine the feasibility of establishing patient-derived organoids from pre-treatment rectal adenocarcinoma biopsies. The primary endpoint is the percent of biopsies that form spherical organoids.

Exploratory Objectives:

1. To describe the radiation response of patient-derived organoids and compare it to the patient's clinical response to neoadjuvant radiation.
2. To describe the radiation response of orthotopic organoid transplants in mice and compare it to the patient's clinical response to neoadjuvant radiation.
3. To describe the histopathologic and molecular characteristics of patient-derived organoids.

Hypotheses

1. 70% of patient-derived organoid attempts will be successful. This protocol will be hypothesis-generating. Data obtained from this protocol will guide future studies on the utility of patient-derived organoids for assessing radiation response in rectal cancer.

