2. BACKGROUND AND SIGNIFICANCE

The standard of care for stage II-III rectal cancer is neoadjuvant chemoradiation or short-course radiation followed by total mesorectal excision.¹ Response to neoadjuvant radiation varies across patients, with some having minimal response to 10-30% having a pathologic complete response. Pathologic complete response is associated with improved clinical outcomes including resectability, sphincter preservation, local control, and overall survival.²⁻⁴ Predicting response to neoadjuvant radiation may inform prognosis and guide more individualized therapy.

Pretreatment markers including gene expression profiles and radiomic features have been investigated but are not used clinically due to limitations such as cost and generalizability.⁵⁻⁷ Preclinical models such as patient-derived tumor cell lines and xenografts have also been used to evaluate individual response to radiation.^{8,9} Limitations of patient-derived cell lines include loss of genetic heterogeneity due to inefficient generation and selective pressure as well as loss of tumor morphology in 2D growth conditions. Patient-derived xenografts retain genetic and phenotypic features, but also have limitations including high resource consumption.

Tumor organoids have emerged as another relevant preclinical model.¹⁰ Organoids grow in a 3D matrix, recapitulate tumor genetic and morphologic features, and have relatively efficient generation and expansion from patient tissue.¹⁰ The Hubrecht Institute generated patient-derived organoids from untreated colorectal cancer in 20 patients with an 80-90% success rate and

demonstrated similar morphology and somatic mutations between primary tumor biopsies and tumor organoids by H&E staining and whole exome sequencing.¹¹

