More recently, several studies have explored the use of tumor organoids to predict response to chemotherapy and radiation, including three colorectal studies published in 2019. A study from the University of Wisconsin generated tumor organoids in multiple cancer types with a 76% success rate for colorectal cancer.¹² Seven primary tumors and corresponding organoids demonstrated similar morphology and mutations by next-generation sequencing, and colorectal cancer organoids had heterogeneous responses to 5-FU and radiation measured by organoid diameter and metabolic imaging. Additionally, as proof-of-principle, organoids from one patient with metastatic colorectal cancer were treated with 5-FU and oxaliplatin to predict whether the patient might respond to retreatment with FOLFOX.¹² Another study from Memorial Sloan Kettering generated rectal cancer organoids from 58 patients, both pre- and post-treatment, with a 77% success rate.¹³ Similar histopathology was demonstrated between primary tumors and corresponding organoids. To demonstrate preserved genetic heterogeneity in the organoids, the mutational landscape across 31 tumor organoids by targeted next-generation sequencing was shown to be similar to that of an independent rectal cancer cohort. Radiation of 19 rectal cancer organoids resulted in varying viability and dose-response curves. In six patients, organoid radiation response measured by the area under the dose-response curve appeared to correlate with patient radiation response measured by pre- and post-radiation tumor size on endoscopy. Four patient organoids were also engrafted into the mouse rectum to create a parallel preclinical model, and 5-FU and FOLFOX response of these transplanted organoids appeared to mirror clinical patient responses.¹³ Lastly, a study from Fudan University collected tumor samples from 112 patients with newly-diagnosed rectal cancer enrolled in a phase III trial (NCT02605265) evaluating the addition of irinotecan to neoadjuvant chemoradiation and generated organoids with a 86% success rate.¹⁴ In line with prior studies, similar histopathology was observed in primary tumors and organoids, and whole exome sequencing in 18 primary tumors and organoids demonstrated similar genomic alterations. For 80 patient-derived organoids, response to 5-FU, irinotecan, and radiation was measured by cell viability and organoid diameter and compared to patient clinical responses. Organoid response to at least one of the treatments generally correlated with patient's AJCC tumor regression grade. However, in 19 patients who had a good response to chemoradiation, the corresponding organoids were actually resistant to radiation, and the authors suggested that in the future, such patients might receive neoadjuvant chemotherapy alone.¹⁴

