For organoid transplantation, organoids will be gently dissociated and resuspended in 3D matrix with minimal medium and injected into the lamina propria of the mouse rectum as previously described.¹⁷ Transplanted tumors will be visible four to six weeks after injection.²⁰ Mice will then receive pelvic radiation of about 20-30 Gy in 4-5 fractions using a single arc, using previously described radiation methods.¹⁸ To measure radiation response, mice will be followed with periodic endoscopy and the percent change in tumor size index after radiation will be measured as previously described.²⁰ The tumor size index is the tumor area divided by the colorectal lumen area. Designated members of the study team with access to the master log will be able to compare the radiation response of organoid transplants with the patient's clinical response to neoadjuvant radiation from the surgical pathology report.

The last exploratory objective will be to describe the histopathology and molecular characteristics of patient-derived organoids. Histopathology may include hematoxylin and eosin staining as well as immunohistochemistry of markers such as CK20, CDX2, and β-catenin. Recent studies have demonstrated a diversity of morphologies in patient-derived organoids that appear to retain characteristics of the primary tumor.¹²⁻¹⁴ Molecular studies may include targeted next-generation sequencing and whole-exome sequencing. Recent studies have used high throughput sequencing to demonstrate that patient-derived organoids also preserve specific mutations compared to the primary tumor biopsy and also have similar total mutational loads and copy number variations.¹²⁻¹⁴ Any findings from organoid histopathology or molecular studies

will not be used for clinical intervention. Only designated members of the study team with access to the master log will be able to make any comparisons between organoid histopathology or molecular studies and patient histopathology or molecular studies.

This protocol involves collection of biopsy samples and analyses of data extracted from the electronic medical record. The variables, endpoint measures, and other data elements that will be extracted include:

- Duke MRN
- Date of birth
- Sex
- Race
- Pathologic diagnosis date
- Clinical TNM stage
- Pre- and post-neoadjuvant therapy proctoscopy findings
- Neoadjuvant radiation therapy dose, fractionation, and dates
- Neoadjuvant chemotherapy type, dose, and dates
- Surgery date

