- Biopsy and surgical pathology findings including histology, microsatellite stability, genomic profiling (e.g. FoundationOne)

Eligible subjects are identified as described below in “Subject Recruitment and Compensation” section, and are selected for inclusion in subsequent analyses based on the criteria described below in the “Selection of Subjects” section.

Timeframe to complete subject identification: 24 months

Timeframe to complete data extraction and entry: 6 months

Timeframe to complete quality assurance check on extracted data: 1 month

Timeframe to complete data analyses: 3 months

Timeframe to complete manuscript and submission to journal: 12 months

Timeframe to disseminate conclusions via conference/meeting, if applicable: 6 months

Timeframe to protocol termination: 36 months

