10. DATA ANALYSIS AND STATISTICAL CONSIDERATIONS

This is a specimen and clinical data collection protocol.

For the primary objective, all enrolled patients are evaluable, and we estimate the evaluable sample size will be 20 patient biopsies. For the exploratory objectives, evaluable patients are

those with successful patient-derived organoids, which we estimate will be about 14 of 20 initial biopsies.

Only descriptive statistical analyses will be performed. The primary objective will be reported as the percent of patient biopsies that form spherical organoids, and the 90% one-sided lower confidence limit will be reported. For instance, if we generate spherical organoids from 14 of 20 (70%) biopsies, the 90% one-sided lower confidence limit will be 56%. Laboratory procedures will follow group standard operating procedures (SOPs). Given the anticipated success rate of generating organoids of about 70%, if we are not successful at generating organoids from 3 of the first 5 patients, we will place the research protocol on hold, and all laboratory SOPs will be reviewed and modified.

The exploratory objectives will be described qualitatively given the anticipated small sample size.¹³ For the organoid radiation dose-response experiments, we will compare the dose-response AUC in patients who did or did not achieve a pCR. For the organoid transplantation experiments, we will compare the percent change in tumor size index in patients who did or did not achieve a pCR.

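### Both exploratory response comparisons rest on pCR yes/no in about 14 patients, so 1.4 to 4.2 pCRs are expected; a graded response should be named alongside it

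*Combined protocol and SAP*

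**What the plan says.** Exploratory objectives 1 and 2 (Section 1) set organoid and transplant radiation response against the patient's clinical response to neoadjuvant radiation. Section 3 takes that clinical response from the surgical pathology report and gives no scale for it.

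Section 10 is more specific. For the organoids, "we will compare the dose-response AUC in patients who did or did not achieve a pCR"; for the transplants, the percent change in tumor size index is split in the same way. The section also states that "The exploratory objectives will be described qualitatively given the anticipated small sample size", and it estimates about 14 evaluable patients from 20 biopsies. Section 1 adds: "This protocol will be hypothesis-generating".

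The extraction list in Section 3 includes "Pre- and post-neoadjuvant therapy proctoscopy findings" and "Biopsy and surgical pathology findings including histology, microsatellite stability, genomic profiling". It names neither a regression grade nor a tumor size measure.

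Section 2 gives a background pCR rate ("10-30% having a pathologic complete response"). It also describes two cited studies that used finer measures of response. One compared organoid response with "AJCC tumor regression grade". The other, reference 13, related organoid AUC in six patients to "patient radiation response measured by pre- and post-radiation tumor size on endoscopy". Section 10 cites that same reference in its sentence on qualitative description.

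**The concern.** A broad objective, the patient's response to radiation, is narrowed in Section 10 to one yes/no split on an outcome that most patients are not expected to reach. Two things follow.

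First, the pCR group may be empty or hold one patient. A descriptive comparison needs no power, but it does need patients on both sides.

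Second, a patient with almost no regression and a patient with near-complete regression count as the same. Whether organoid sensitivity follows the degree of response cannot be seen from such a split.

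These two comparisons are the plan's only named link between laboratory response and patient response, and the data are meant to guide later work on that link. The primary endpoint, the description of organoid and transplant radiation response itself, and exploratory objective 3 do not depend on the split.

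**Working it through.** **Inputs.** 20 biopsies and about 14 evaluable patients (Section 10); 70% organoid success (Section 1); pCR rate 10-30% (Section 2, a background range and not a design assumption for this cohort). The 20% rate below is the midpoint of that range.

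**The plan's own figure.** 20 × 0.70 = 14, as stated.

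**Expected pCRs.** 14 × 0.10 = 1.4; 14 × 0.20 = 2.8; 14 × 0.30 = 4.2.

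**Chance of few pCRs.** With X ~ Binomial(14, p), P(X = 0) = (1 − p)^14 and P(X ≤ 1) = (1 − p)^14 + 14p(1 − p)^13. At p = 0.10 this is 0.229 + 0.356 = 0.585.

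| pCR rate | P(none) | P(0 or 1) | P(at most 2) |
|---|---|---|---|
| 10% | 22.9% | 58.5% | 84.2% |
| 20% | 4.4% | 19.8% | 44.8% |
| 30% | 0.7% | 4.7% | 16.1% |

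**Letting organoid success vary.** With X ~ Binomial(20, 0.7p), P(0 or 1) is 58.7%, 20.8% and 5.7%, so fixing 14 makes little difference.

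**Transplants.** The documents give no rate of successful transplantation. If 12 patients have a measurable transplant (assumed), P(0 or 1) is 66%, 27% and 9%; if 10 (assumed), it is 74%, 38% and 15%.

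**Precision of the split.** The standard error of a difference in means, in SD units, is √(1/k + 1/(14 − k)) with k pCRs: 1.04 for k = 1, 0.76 for k = 2, 0.59 for k = 4, against 0.53 for an even 7:7 split.

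**What a grade could add (illustration only; the plan sets no test, alpha or power).** Simulation of 6,000 trials per cell: n = 14, bivariate normal laboratory and clinical response, and an assumed four-level grade with non-pCR patients in equal thirds. The pCR split uses an exact Mann-Whitney test and the grade uses Spearman (t approximation), both two-sided 5%. Ranges run over pCR rates of 10-30%.

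| True correlation | pCR split | Grade | Grade, 20% misread by one level |
|---|---|---|---|
| 0.3 | 4-9% | 15-16% | 14% |
| 0.5 | 8-23% | 37-38% | 32-34% |
| 0.7 | 18-47% | 73% | 64-66% |

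Part of the gap is conservatism of the exact test: with no association it rejects 2-4% of the time, against about 5% for Spearman. A less favorable grade distribution (non-pCR patients split 15/75/10%, 20% misread) at correlation 0.7 gives 44%, 52% and 57% for grade against 18%, 36% and 46% for the pCR split, at pCR rates of 10%, 20% and 30%.

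**Precision of a rank correlation.** For an observed 0.5, Fisher's z = 0.549 with variance 1.06/(14 − 3) = 0.0964, so SE = 0.310. The limits on the z scale are 0.549 ± 1.96 × 0.310, which back-transform to about −0.06 and 0.82.

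**The case against.** The plan is candid about its limits: exploratory, qualitative, small. No test or decision depends on the pCR split, so a listing of one patient against 13 is weak but not wrong. The objectives and Section 3 speak of clinical response in general, and Section 10 does not call pCR the sole contrast. The pathology item in the extraction list is open-ended and could already take in a regression grade. pCR is also a sound anchor, since Section 2 ties it to clinical outcomes. The 10-30% rate is background, and at 20% or above two or more pCRs would be seen in about 80% of such studies or more (100% − 19.8% = 80.2%).

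Much of this stands. It rules out calling the matter a power failure, and it means the detection figures are illustration, not evidence of a defect. A high true correlation has no support in the documents: Section 2 reports 19 patients in one cited study with a good chemoradiation response but radiation-resistant organoids. In the present study too, patients may receive chemotherapy while the organoids receive radiation alone. That mismatch affects pCR as much as any grade.

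It does not remove the concern. The wider wording elsewhere names no scale, so nothing ensures that a grade will be extracted or used. Calling a contrast descriptive does not help when one side has nobody in it. One further caveat is fair: the documents do not say that the site's pathology reports carry a regression grade or that proctoscopy notes record size, so a graded response could be derived only where they do.

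**Conclusion.** The concern holds and is worth acting on, as an improvement to the exploratory analysis. With 14 evaluable patients and pCR rates of 10-30%, 1.4 to 4.2 pCRs are expected, and the chance that the planned split has nobody or one patient on one side runs from 58% down to 5%. The problem is serious near the low end of the range and slight near the high end. If transplants are measurable in fewer patients, it is worse for that comparison.

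The result rests on the plan's 70% organoid success, its background pCR range, and independence between patients. It also takes every evaluable patient to have surgical pathology; the documents give no rate for patients who do not reach surgery. The gain from a grade is small if the true correlation is low, and 14 patients give an imprecise correlation in any case.

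**What to change.** - **Section 3:** name tumor regression grade in the surgical pathology extraction item.
- **Section 10:** describe organoid AUC and percent change in tumor size index against that ordinal grade, with a patient-level plot and a rank correlation (Kendall or Spearman) with its confidence interval, labelled descriptive and hypothesis-generating.
- Mark each patient's neoadjuvant regimen, already extracted, on the plot.
- Use proctoscopic change as a supporting measure where size is recorded.
- Keep pCR yes/no as a descriptive comparison and report the number in each group and the number of patients without a grade.

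The cost is one extracted field and two or three sentences, with no extra patients or procedures. The downsides are reader variability in grade, reports that may lack a grade, and proctoscopic size that may not be recorded for every patient.

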11. DATA SAFETY AND MONITORING

This clinical research study will be monitored both internally by the PI, and institutionally by the Duke Cancer Institute (DCI). In terms of internal review the PI will continuously monitor and tabulate adverse events. Appropriate reporting to the Duke University Medical Center IRB will be made. If an unexpected frequency of Grade III or IV events occur, depending on their nature, action appropriate to the nature and frequency of these adverse events will be taken. This may require a protocol amendment, dose de-escalation, or potentially closure of the study. The PI of this study will also continuously monitor the conduct, data, and safety of this study to ensure that:

- Interim analyses occur as scheduled;
- Stopping rules for toxicity and/or response are met;
- Risk/benefit ratio is not altered to the detriment of the subjects;
- Appropriate internal monitoring of AEs and outcomes is done;
- Over-accrual does not occur;
- Under-accrual is addressed with appropriate amendments or actions;
- Data are being appropriately collected in a reasonably timely manner.

DCI Protocol Review and Monitoring systems (PRMS) review of this protocol begins with an initial review by the Cancer Protocol Committee (CPC). CPC new protocol review focuses on scientific relevance, study design, adequacy of biostatistical input, protocol prioritization, feasibility of completing the study within a reasonable time frame and risk assessment of the trial. The PI will abide by CPC assessment of the level of risk, which will determine the intensity of subsequent DCI monitoring. CPC also conducts annual scientific progress reviews on protocols that are open to enrollment and focus on protocol prioritization, accrual and scientific progress. These reviews are conducted at the time of IRB annual renewals and documentation of all CPC reviews will be maintained in eIRB/iRIS systems.

A determination for the degree of monitoring conducted by the DCI monitoring team is made at the time of initial CPC approval to commensurate with the type and level of intervention, phase, endpoints, degree of risk, size and complexity of the protocol. A formal, independent monitoring will be conducted by the DCI monitoring team according to the risk level and monitoring plan assigned by the CPC until the study is closed to enrollment or subjects are no longer receiving study drug or other interventions that are more than minimal risk. Additional monitoring may be prompted by findings from monitoring visits, unexpected frequency of serious and/or unexpected toxicities, or other concerns. Monitoring visits may also be initiated upon request by DUHS and DCI Leadership, CPC, SOC, a sponsor, an investigator, or the IRB.

The DCI monitoring team reviews the adequacy of informed consent, enrollment of eligible patients, implementation of protocol-specified procedures and treatment, adequacy of data collection, and appropriateness of adverse event monitoring and reporting. The DCI monitoring team presents final monitoring reports to the DCI Safety Oversight Committee (SOC) highlighting safety concerns and unresolved issues. The SOC, at a convened meeting, assigns an overall rating of satisfactory, marginal, or unsatisfactory to reflect the overall quality of data, regulatory, consent, eligibility, study conduct and AE reporting. Corrective action plans (CAPs) are developed, implemented, and evaluated as indicated. The SOC will notify the sponsor-investigator and DUHS IRB when significant safety concerns are identified.

The SOC in concert with DCI monitoring team conducts data and safety monitoring for DUHS sponsor-investigator phase I and II, therapeutic interventional oncology studies that do not have an independent DSMB. These reviews occur at a minimum every 6 months and more frequently for the high risk studies. The SOC safety reviews include review of safety data, enrollment status, stopping rules if applicable, accrual, toxicities, reference literature, and interim analyses as provided by the sponsor-investigator. The SOC, at a convened meeting, assigns a rating of satisfactory when adequate accrual with lack of excessive toxicity is present.

12. PRIVACY, DATA STORAGE, AND CONFIDENTIALITY

The Principal Investigator will ensure that subject privacy and confidentiality of the subject's data will be maintained. RDSPs will be approved by the appropriate institutional Clinical Research Unit.

To protect privacy, every reasonable effort will be made to prevent undue access to subjects during the course of the study. Prospective participants will be consented in a private room or by telephone, if using e-consent. All research related interactions with the participant will be conducted by qualified research staff who are directly involved in the conduct of the research study.

To protect confidentiality, subject files in paper format will be stored in secure cabinets under lock and key accessible only by the research staff. Subjects will be identified only by a unique study number and subject initials. Electronic records of subject data will be maintained using a dedicated REDCap database which is housed in an encrypted and password-protected Duke file server. Access to electronic databases will be limited to the PI and members of the study team. Subject data may be stored temporarily on encrypted and password-protected portable memory devices such as flash drives and external hard drives, but only when absolutely necessary. Data

stored on portable memory devices will be de-identified. Subject data will be deleted from the portable memory device at the earliest opportunity. The security and viability of the IT infrastructure will be managed by the DCI and/or Duke Medicine.

Any cell lines or organoids derived from the patient samples will be given a unique de-identified reference code and will not contain any subject PHI. A secure master log document linking the patient identification and specimen information will be generated during specimen collection. Only the PI and designated members of the study team will have access to the master log.

Upon completion of the study, research records will be archived and handled per DUHS HRPP policy.

Subject names or identifiers will not be used in reports, presentations at scientific meetings, or publications in scientific journals.

